6.4 Treatment compliance

Any change from the dosing schedule or dose discontinuations should be recorded in the eCRF.

The IP Storage Manager is responsible for managing the IP from receipt by the study site until the destruction or return of all unused IP. The date and time of all IP administrations, as well as any missed doses, should be recorded in the appropriate section of the eCRF.

6.5 Concomitant therapy

All ICS asthma medications taken in the 12 months prior to Visit 1 must be recorded in the eCRF along with reason for treatment.

To satisfy inclusion criteria 6, a history of continuous treatment with medium or high dose ICS plus a second controller medication for at least 3 months prior to Visit 1 should be documented in source and recorded in the eCRF prior to the date of randomization.

In order to satisfy inclusion criterion 7, a history of all asthma controller medications for the 3 months prior to Visit 1 until the end of the study should be documented in source and recorded in the eCRF. No changes are allowed to background asthma medications throughout the duration of the study except during the treatment of an asthma exacerbation.

All other medications taken for conditions other than asthma in the 3 months prior to Visit 1 must be recorded in the eCRF along with reason for treatment by the Investigator/authorized delegate at each visit (as shown in [Table 1](#) and [Table 2](#)).

Maintenance asthma medication is not regarded as an IP, but will be provided/reimbursed by AstraZeneca according to local regulations in order to maintain appropriate oversight and access to this concomitant therapy.

As theophylline has a narrow therapeutic window, please note that subjects on maintenance treatment with theophylline should have blood concentration levels within therapeutic range documented before Visit 1. If this is not documented before signing the informed consent, it can be obtained after informed consent has been given or as part of the Visit 1 procedures. The sample can be analysed at the central or local lab as applicable. Investigator can use their time and other factors that may impact the results. Investigator can use their clinical judgement about the therapeutic range of theophylline levels on the basis of sampling time and other factors that may impact the results.

Any medication or vaccine including over-the-counter or prescription medicines, vitamins, and/or herbal supplements that the subject is receiving at the time of enrolment or receives during the study must be recorded along with:

- Reason for use
- Dates of administration including start and end dates

Table 6 Restricted medications

Medication/class of drug:	Usage

Maintenance treatment with ICS and long-acting bronchodilators (including ICS/LABA combinations)
	
No changes in either dose or regimen are allowed from V1 and throughout the IP treatment and preferably 4 weeks after the last dose of IP.
 
The patients should be instructed not to take their usual asthma controller medication (i.e., LABA) prior to scheduled ECG assessment (please refer below for long-acting bronchodilator restrictions). Use of SABA should be avoided within 6 hours before ECG assessments. The medication restrictions are waived for the screening ECG at Visit 1.
 
Twice daily bronchodilators should be withheld for at least 12 hours prior to the scheduled FENO and spirometry at site.
 
Once daily bronchodilators should be withheld for at least 24 hours prior to the scheduled FENO and spirometry at site.
 
Subjects will not need a washout of their asthma medications for unscheduled visits due to asthma worsening.

Short-acting beta-agonists (SABA)
	
Regular scheduled use of SABA is not allowed from V1 and throughout the IP treatment and preferably 4 weeks after the last dose of IP, PRN use is allowed if needed, however attention should be paid to the following restrictions.
 
SABA should be withheld for at least 6 hours prior to scheduled spirometry, FENO, ECG at site with the exception of any unscheduled visits due to asthma worsening.
 
When possible, home PEF and domiciliary FENO assessments should be taken after the SABA is withheld for at least 6 hours.

Table 6 Restricted medications

Medication/class of drug:	Usage

Additional Maintenance Controllers
	
No changes in either dose or regimen are allowed from V1 and throughout the IP treatment and preferably 4 weeks after the last dose of IP.
 
Once daily LABA and LAMA should be withheld for at least 24 hours prior scheduled spirometry and FENO at site visits with the exception of any unscheduled visits due to asthma worsening.
 
Twice daily LABA or LAMA containing therapies should be withheld for at least 12 hours prior to scheduled spirometry and FENO at site with the exception of any unscheduled visits due to asthma worsening.
 
LTRA should be restricted for at least 24 hours prior to scheduled spirometry and FENO at site with the exception of any unscheduled visits due to asthma worsening.
 
Subjects on theophylline should have blood concentration levels within therapeutic range documented before proceeding in the study.
 
Twice daily theophyllines should be withheld for at least 12 hours prior to scheduled spirometry and FENO at site with the exception of any unscheduled visits due to asthma worsening.
 
Once daily theophyllines should be withheld for at least 24 hours prior to scheduled spirometry and FENO at site with the exception of any unscheduled visits due to asthma worsening.

Short-acting anticholinergics (e.g. ipratropium)
	
These are not allowed as a rescue treatment for worsening asthma symptoms from V1 and throughout the IP treatment and preferably 4 weeks after the last dose of IP . They may be used for managing an asthma exacerbation event.

Table 6 Restricted medications

Medication/class of drug:	Usage
Inactive/killed vaccinations (e.g. inactive influenza)	Allowed provided they are not administered within 5 days before or after any study visit.
Allergen Immunotherapy	Allowed, if on stable therapy for at least 2 months prior to date of Visit 1 with no anticipated change during the treatment period. These should not be administered on the same day as IP administration.

Table 7 Prohibited medications

Prohibited medication/class of drug:	Usage
Long-acting beta-agonists as a reliever (e.g. Symbicort Maintenance and Reliever Treatment)	Not allowed 15 days prior to Visit 1, during screening/run-in and throughout the IP treatment and preferably 4 weeks after the last dose of IP.
Suplatast tosilate (T2 cytokine inhibitor)	Not allowed within 15 days prior to Visit 1, during screening/run-in and throughout the IP treatment and preferably 4 weeks after the last dose of IP.
Live Attenuated Vaccines	Not allowed 30 days prior to the date of randomization, and during the study including the follow-up period.
Any immunomodulators or immunosuppressives (except for OCS used in the maintenance treatment of asthma, asthma exacerbations in screening/run-in, and protocol defined asthma exacerbations on or after Visit 3)	Not allowed 12 weeks prior to randomization, during screening/run-in and throughout the IP treatment and preferably 4 weeks after the last dose of IP.
Immunoglobulin or blood products	Not allowed 30 days prior to Visit 1, during screening/run-in and throughout the IP treatment and preferably 4 weeks after the last dose of IP.
Any marketed (e.g. omalizumab, mepolizumab, reslizumab) or to be marketed or investigational biologic treatment	Not allowed 4 months or 5 half-lives (whichever is longer) prior to the date of Visit 1, throughout the entire, screening run in period, treatment period (even if the subject has discontinued IP) and until the follow up visit week 64.
Other investigational products (including investigational use of an approved drug)	Not allowed 30 days or 5 half-lives (whichever is longer) prior to Visit 1, during screening/run-in and throughout the IP treatment and until the follow up visit week 64.

Table 7 Prohibited medications

Prohibited medication/class of drug:	Usage
Herbal remedies for the treatment of allergic, inflammatory, or respiratory diseases	Not allowed 30 days prior to Visit 1, during screening/run-in and throughout the IP treatment and preferably 4 weeks after the last dose of IP.
Medications not currently licensed for use in the treatment of asthma, for example medications approved for Chronic Obstructive Pulmonary Disease and not part of current standard of care	Not allowed 30 days prior to Visit 1, during screening/run-in and throughout the IP treatment and preferably 4 weeks after the last dose of IP.

6.5.1 Other concomitant treatment

Other medication other than that described above, which is considered necessary for the subject's safety and well-being, may be given at the discretion of the Investigator and recorded in the appropriate sections of the Case Report Form.

6.5.2 Rescue Medication Use

SABA should be withheld for at least 6 hours prior to scheduled site visit spirometry, FENO, ECG at site with the exception of any unscheduled visits due to asthma worsening. When possible, home lung function and domiciliary FeNO measurements should be taken at least 6 hours after the last dose of SABA rescue medication.

Albuterol (US)/salbutamol (ex US) rescue medication will be provided by the sponsor and obtained locally.

Regularly scheduled SABA use in the absence of any asthma symptoms is not allowed from enrolment (Visit 1) and throughout the study duration. Prophylactic use of SABA (e.g. prior to planned exercise) or any other use than to curb worsening of asthma symptoms should be documented in medical notes and entered in the eCRF. Any such prophylactic use of SABA must not be recorded in the Asthma Daily Diary.

Rescue use of SABA administered via nebulization is discouraged, except as urgent treatment during an asthma exacerbation. Occasions where SABA is administered via nebulization will be recorded separately from metered dose inhaler inhalations in the eDiary.

6.5.3 Bronchial Thermoplasty

Subjects should not be treated with bronchial thermoplasty during the study.

6.6 Dose modification

N/A

6.7 Treatment after the end of the study

Subjects who complete week 64 should be given standard of care at the discretion of the investigator. Subjects that are eligible and decide to enroll in a separate extension study will not attend the follow-up visits at week 58 and week 64 and should comply with the requirements of the separate extension study protocol.

7. DISCONTINUATION OF TREATMENT AND SUBJECT WITHDRAWAL

7.1 Discontinuation of study treatment

Subject may be discontinued from IP in the following situations.

Note that discontinuation from study treatment does NOT mean complete withdrawal from the study.

- Subject decision. The subject is at any time free to discontinue IP, without prejudice to further treatment
- An adverse event considered to jeopardise the safety of a subject participating in the study
- Pregnancy
- Severe non-compliance with the Clinical Study Protocol
- Development of any study specific criteria for discontinuation, including:
 - An anaphylactic reaction to the IP requiring administration of epinephrine
 - A helminth parasitic infestation requiring hospitalization
 - An asthma-related event requiring intubation
 - Any malignancy except subjects who develop basal cell carcinoma or localized squamous cell carcinoma of the skin, provided that the malignancy is excised and determined to have clean margins
- Development of one or more of the following:
 - Confirmed ALT or AST increase of ≥ 8 x ULN
 - Confirmed ALT or AST increase of ≥ 5 x ULN for more than 2 weeks
 - Confirmed ALT or AST increase of ≥ 3 x ULN and total bilirubin of ≥ 2 x ULN

- ALT or AST of ≥ 3 x ULN with the appearance of fatigue, nausea, vomiting, right upper quadrant pain or tenderness, fever, rash, and/or eosinophilia ($\geq 5\%$)

See the SoA for data to be collected at the time of IP discontinuation and follow-up and for any further evaluations that need to be completed.

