- j All ICS medications in the 12 months prior to Visit 1 must be recorded in the eCRF along with reason for treatment. To satisfy inclusion criteria #6 and #7, the history of continuous treatment with ICS plus second controller medication for at least 3 months prior to Visit 1 should be documented in source and recorded in the eCRF prior to the date of randomization. All other medications taken for conditions other than asthma in the 3 months prior to Visit 1 must be recorded in the eCRF along with reason for treatment.
- k All total serum IgE, IgA, IgG and IgM results will be redacted from the central laboratory reports except Visit 1, at Visit 3 prior to IP administration and any repeat testing that is performed during the screening/run-in period.
- l FSH test done only in women < 50 years who have been amenorrheic for > 12 months to confirm postmenopausal status.
- m FENO test needs to be completed prior to spirometry. FENO is to be completed at either Visit 2 or Visit 2a.
- n Domiciliary FENO only for those subjects who have opted in at consent. The home FENO device will be dispensed at V2 once all spirometry criteria are met for this visit. If an optional V2a is required, then the home FENO device will be dispensed at this visit once all spirometry criteria are met.
- o dECG to be completed prior to any blood draws.
- p Eosinophils, basophil and monocyte counts will be redacted from the central laboratory reports except Visit 1, at Visit 3 prior to IP administration and any repeat testing that is performed during the screening/run-in period.
- q If Visit 1 is conducted more than 35 days in advance of Visit 3, the Visit 2 and Visit 2a visit window is adjusted to complement the preceding visit date (Visit 1).

Table 2 Schedule of Assessments-Randomization, treatment period (Wk 0 - Wk 52), follow-up (Wk 58 - Wk 64)

	Random-ization	Treatment														EOT Period ^w	IPD ^q	FU	FU	UNS ^v	Details in CSP section or Appendix
Visit	3	4	5	6	7	8	9	10	11	12	13	14	15	16	17		18	19		Details in CSP section or Appendix	
Week	0	2	4	8	12	16	20	24	28	32	36	40	44	48	52		58	64			
Day (visit window)	0	±3	±5	±5	±5	±5	±5	±5	±5	±5	±5	±5	±5	±5	±5		±7	±7			
Procedures																					
Inclusion /exclusion criteria	X																			Section 5.1 and 5.2	
Height ^a															X	X				Section 8.2.2	
Weight								X							X	X				Section 8.2.2	
Health care resource Utilization ^b	X	X	X	X	X	X	X	X	X	X	X	X	X	X	X	X	X	X	X	Section 8.9	

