Serum for ADA and nAb	X		X		X			X			X				X	X		X		Section 8.5	
Serum for PK ^u	X		X		X			X			X				X	X		X		Section 8.6	
IgE (FEIA)	X																			Section 8.8.2	
Total immunoglobulin (IgE, IgA, IgG, IgM) ^k	X	X	X		X			X			X				X	X		X	X	Section 8.8.2	
Serum for biomarker analysis	X	X	X		X			X			X				X	X		X	X	Section 8.8	
Blood sample for DNA (optional) ⁿ	X							X							X			X		Section 8.7.1	
Blood samples for RNA transcriptome profiling	X	X	X		X			X							X			X	X	Section 8.8.3	
Flow Cytometry ^s	X							X							X					Section 8.8.4	
Lung Function Assessments																					
Spirometry (pre-BD FEV1, FVC and FEV1/FVC) ^o	X	X	X	X	X	X		X			X				X	X	X	X	X	Section 8.1.2	
Post-BD FEV1, FVC and FEV1/FVC)	X							X							X	X			X	Section 8.1.2.2	
Home peak flow compliance and technique check	X	X	X	X	X	X	X	X	X	X	X	X	X	X	X	X				Section 8.1.3	

	Random-ization	Treatment														EOT Period ^w	IPD ^a	FU	FU	UNS ^v	Details in CSP section or Appendix
Visit	3	4	5	6	7	8	9	10	11	12	13	14	15	16	17		18	19		Details in CSP section or Appendix	
Week	0	2	4	8	12	16	20	24	28	32	36	40	44	48	52		58	64			
Day (visit window)	0	±3	±5	±5	±5	±5	±5	±5	±5	±5	±5	±5	±5	±5	±5		±7	±7			
Home assessment of PEF	Measurements every morning and evening throughout treatment period																			Section 8.1.3	
Study treatment administration																					
Randomization	X																			Section 6.1	
Administration of IP ^p	X		X	X	X	X	X	X	X	X	X	X	X	X						Section 6.2	

- ^a Only to be measured for the adolescent subject.
- ^b Asthma specific resource utilization (eg unscheduled physician visits, unscheduled phone calls to physicians, use of other asthma medications).
- ^c ACQ-6 to be completed before AQLQ(s)+12.
- ^d SNOT-22 questionnaire will only be completed during the treatment period for those subjects who have completed SNOT-22 at Visit 2.
- ^e Daily Diary: Asthma Symptom Diary (ASD), and items related to: Rescue medication use, Global asthma severity, Night time awakenings, Adherence to maintenance medication.
- ^f PGI-C will not be collected at Visit 3.
- ^g ECG must be collected prior to any blood draws, spirometry, BD administration and IP administration.
- ^h All blood sampling should be done prior to IP administration.
- ⁱ Eosinophils, basophil and monocyte counts will be redacted from the central laboratory reports except Visit 1, at Visit 3 prior to IP administration and any repeat testing that is performed during the screening/run-in period.

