The study will randomize approximately 1060 subjects globally in a 1:1 ratio to either tezepelumab or placebo. Approximately 80 adolescents aged 12 to 17 years, will be included as subjects. The subjects will be stratified by region and age (adult/adolescents).

All subjects must have been on a medium to high dose ICS for at least 3 months prior to screening (see [Appendix F](#) for definitions of medium to high dose ICS) and have been on at least one asthma controller medication with or without OCS in the 3 months prior to date of informed consent as per inclusion criteria 6 and 7.

The total study population will be monitored to ensure a broad subject distribution across 3 different key clinical factors. Approximately 20% of the total study population will be subjects who are treated with a total daily dose of medium dose ICS as well as on at least one additional maintenance asthma controller medication with or without OCS in the previous 3 months prior to date of informed consent.

Approximately 40% of subjects in the study will be required to have had at least 3 exacerbations in the past 12 months, with the remaining subjects having had exactly 2 exacerbations. Details on acceptable documentation is specified in section 8.1.1.

The study will also aim to randomize a similar percentage of subjects with <300 eosinophils/ μl and ≥ 300 eosinophils/ μl . In addition, a reasonable number of subjects is expected to be randomized with < 150 eosinophils/ μl and > 450 eosinophils/ μl .

The anticipated percentages for the factors above may be applied to the adult population instead of the overall population to avoid difficulties with adolescent recruitment, if necessary. When the target percentage of subjects for the ICS, exacerbations or eosinophil subgroup in a region is reached, consideration will be given to closing the IWRS/IVRS randomization for that subgroup, which may be done either overall or within a specific region. Once a subgroup is closed, subjects in the screening/run-in period in the closed subgroup will not be allowed to be randomized and will be screen failed.

Section 6.5 ([Table 6](#) and [Table 7](#)) provides a list of medication restrictions and prohibitions to be followed throughout the conduct of the clinical trial.

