8. STUDY ASSESSMENTS AND PROCEDURES

Study procedures and their timing are summarized in the SoA.

The investigator will ensure that data are recorded on the electronic Case Report Forms (CRFs). The Web Based Data Capture (WBDC) system will be used for data collection and query handling.

The investigator ensures the accuracy, completeness, legibility and timeliness of the data recorded and of the provision of answers to data queries according to the Clinical Study Agreement. The investigator will sign the completed electronic CRFs. A copy of the completed electronic CRFs will be archived at the study site. Additional data to assess the impact of COVID-19 pandemic will be collected.

Immediate safety concerns should be discussed with the sponsor immediately upon occurrence or awareness to determine if the subject should continue or discontinue study treatment.

Adherence to the study design requirements, including those specified in the SoA, is essential and required for study conduct.

All screening evaluations must be completed and reviewed to confirm that potential subjects meet all eligibility criteria. The Investigator will maintain a screening log to record details of all subjects screened and to confirm eligibility or record reasons for screening failure, as applicable.

The amount of blood collected from each subject over the duration of the study (excluding optional blood samples) will be approximately 220 mL, including any extra assessments that may be required, will not exceed 450 mL. Repeat or unscheduled samples may be taken for safety reasons or for technical issues with the samples.

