8.2.1 Clinical safety laboratory assessments

See [Table 8](#) for the list of clinical safety laboratory tests to be performed, and the SoA for the timing and frequency. All protocol-required laboratory assessments, as defined in the table, must be conducted in accordance with the laboratory manual and the SoA.

The Investigator should make an assessment of the available results with regard to clinically relevant abnormalities. The laboratory results should be signed and dated and retained at centre as source data for laboratory variables.

For information on how AEs based on laboratory tests should be recorded and reported, see [Section 8.3.7](#).

The clinical chemistry, haematology and urinalysis will be performed at a central laboratory.

Table 8 Laboratory safety variables

Haematology/Haemostasis (whole blood)	Clinical Chemistry (serum or plasma)
B-Haemoglobin (Hb)	S-Alkaline phosphoatase (ALP)
B-Leukocyte count	S-Alanine transaminase (ALT)
B-Leukocyte differential count (absolute count)	S-Aspartate transaminase (AST)
B-Platelet count	S-Bilirubin, total
B-Hematocrit	S-Blood urea nitrogen
B-Mean Corpuscular Volume	S-Calcium, total
B-Red blood cell (RBC) count	S-Chloride
	S-Creatinine
Urinalysis (dipstick)	S-Creatinine kinase (CK)
U-Hb/Erythrocytes/Blood	S-CRP
U-Protein/Albumin	S-Gamma-glutamyl transpeptidase (GGT)
U-Glucose	S-Glucose
	S-Phosphorus
U-Microscopy and culture as required*	S-Potassium
	S-Sodium
	S-Total cholesterol
	S-Uric acid

*Urine samples will be analyzed locally and sent to the central laboratory only for analysis when a positive dipstick result for any parameter is observed.

NB. In case a subject shows an AST **or** ALT $\geq 3 \times \text{ULN}$ together with total bilirubin $\geq 2 \times \text{ULN}$ please refer to [Appendix E](#) for further instructions.

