AST or ALT $\geq 3 \times$ ULN **together with** TBL $\geq 2 \times$ ULN, where no other reason, other than the IMP, can be found to explain the combination of increases, e.g., elevated ALP indicating cholestasis, viral hepatitis, another drug.

For PHL and HL the elevation in transaminases must precede or be coincident with (i.e., on the same day) the elevation in TBL, but there is no specified timeframe within which the elevations in transaminases and TBL must occur.

E 3 Identification of potential Hy's Law cases

In order to identify cases of PHL it is important to perform a comprehensive review of laboratory data for any subject who meets any of the following identification criteria in isolation or in combination:

- $ALT \geq 3 \times ULN$
- $AST \geq 3 \times ULN$
- $TBL \geq 2 \times ULN$

Central laboratories being used:

When a subject meets any of the PHL identification criteria, in isolation or in combination, the central laboratory will immediately send an alert to the Investigator (and also to AstraZeneca representative).

The Investigator will also remain vigilant for any local laboratory reports where the PHL identification criteria are met, where this is the case the Investigator will:

- Notify the AstraZeneca representative
- Request a repeat of the test (new blood draw) by the central laboratory
- Complete the appropriate unscheduled laboratory CRF module(s) with the original local laboratory test result

When the identification criteria are met from central or local laboratory results the Investigator will without delay:

- Determine whether the subject meets PHL criteria (see section 2 within this Appendix for definition) by reviewing laboratory reports from all previous visits (including both central and local laboratory results)

E 4 Follow-up

E 4.1 Potential Hy's Law criteria not met

If the subject does not meet PHL criteria the Investigator will:

- Inform the AstraZeneca representative that the subject has not met PHL criteria.

- Perform follow-up on subsequent laboratory results according to the guidance provided in the Clinical Study Protocol.

E 4.2 Potential Hy's Law criteria met

If the subject does meet PHL criteria the Investigator will:

- Notify the AstraZeneca representative who will then inform the central Study Team

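### The eosinophilia limb of the Section 7.1 liver stopping criterion cannot be assessed from the redacted central reports, and nobody is assigned to read the value

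*Protocol*

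**What the plan says.** Protocol Section 7.1 introduces its stopping grounds with "Subject may be discontinued from IP in the following situations" and includes four liver criteria. Three rest on chemistry alone: confirmed ALT or AST ≥8×ULN; confirmed ≥5×ULN for more than 2 weeks; and confirmed ≥3×ULN with total bilirubin ≥2×ULN. The fourth is ALT or AST ≥3×ULN "with the appearance of fatigue, nausea, vomiting, right upper quadrant pain or tenderness, fever, rash, and/or eosinophilia", with eosinophilia set at ≥5%.

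Protocol Section 1.1, Table 2, footnote i, attached to the haematology row, states: "Eosinophils, basophil and monocyte counts will be redacted from the central laboratory reports except Visit 1, at Visit 3 prior to IP administration". Repeat tests in screening/run-in are also exempt. Table 1, footnote p, carries the same rule. The Table 2 row covers the treatment visits, the IP discontinuation visit, Week 64 and unscheduled visits.

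Protocol Section 8.2.1 places haematology at a central laboratory, and its Table 8 lists the differential as absolute counts.

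Protocol Appendix E 3 says that when ALT or AST is ≥3×ULN, or bilirubin ≥2×ULN, "the central laboratory will immediately send an alert to the Investigator", with a copy to the sponsor's representative. Eosinophils are not part of that alert. Section 8 asks for immediate safety concerns to be discussed with the sponsor "to determine if the subject should continue or discontinue study treatment".

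**The concern.** The protocol gives the investigator a safety rule and withholds one of the results needed to apply it. The subject concerned has ALT or AST ≥3×ULN after dosing, none of the listed symptoms, bilirubin below 2×ULN, and neither higher transaminase threshold met. For that subject eosinophilia is the only liver criterion that can still apply.

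The site then has two choices. It can leave the limb unchecked. Or it can order a local differential and see a count that the redaction was presumably meant to keep from it. Peripheral blood eosinophils are a secondary biomarker outcome (Protocol Section 3), so this is a value the trial has reason to protect.

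There is a reporting side too. SAP Section 2.2 has an important-deviation category for subjects who developed discontinuation criteria but stayed on IP. A site could fall into it without being able to know. Whether a permissive criterion counts there depends on the Protocol Deviations Plan, which is not among the documents.

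**Working it through.** The plan states no figure to reproduce. The check sets the provisions side by side and looks for any route by which the eosinophil value reaches someone who is to act on it.

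**1. Is eosinophilia sufficient alone?** Yes. The list in the fourth criterion ends in and/or, so any one feature completes it.

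**2. Is the value on the reports the site receives?** Not after the Visit 3 pre-dose sample. The exceptions in footnote i are all before dosing, and the footnote covers the whole row, including the unscheduled column.

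**3. Can the site derive it from what remains?** Write L for leukocytes, N for neutrophils, Ly for lymphocytes, and E, B, M for eosinophils, basophils and monocytes. The site can form

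L − N − Ly = E + B + M.

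Three redacted cell types share one remainder. If the remainder is below 5% of L, then E is below 5% and eosinophilia is ruled out. If it is 5% or more, E is undetermined. Example with assumed values (×10⁹/L): 6.0 − 3.6 − 1.8 = 0.6, and 0.6 / 6.0 = 10%. Eosinophils could lie anywhere from 0% to 10%. Because Table 8 gives absolute counts, no separate percentage is available.

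**4. Does another provision supply the answer?**
- Appendix E 3: the alert covers ALT, AST and bilirubin only.
- Appendix E 4.1: if potential Hy's Law is not met, follow-up goes back to protocol guidance, and E 1 says that guidance is in Section 7.1. The path is circular for this limb.
- Appendix E6: the recommended follow-up tests include no differential.
- Section 8.4.6: the DSMB reviews cumulative safety data with an adolescent focus. It is not given individual stopping decisions.
- Section 6.3: the sponsor's Patient Safety department holds the randomization list, but is not asked to read eosinophils.
- Table 2, footnote l, states who is blinded to post-randomization FENO. No such statement is made about the sponsor and eosinophils.

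**5. How many subjects?** The documents give no frequency of ALT or AST ≥3×ULN. Under an assumed 0.5% to 2%:

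0.005 × 1060 = 5.3 and 0.02 × 1060 = 21.2.

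This is a ceiling of about 5 to 21 subjects. Those with a listed symptom, raised bilirubin or a higher threshold met must come out, as must those without newly appearing eosinophilia. The documents do not allow that remainder to be estimated, but it is small.

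**The case against.** The best reply is that the redaction applies to central reports only. Nothing forbids a local differential, and Appendix E 1 accepts local results for Hy's Law work. The sponsor receives the same alert, Section 8 sends safety concerns to it, and an already unblinded function exists. Section 7.1 is permissive, and a separate ground allows stopping for any adverse event judged to jeopardise safety, so no subject is prevented from stopping. The laboratory manual was not supplied and may say more.

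Most of this stands. A reader might infer that the whole criterion is unusable; that is not supported, because the symptom limbs work and a local test is possible. What remains is that no provision gives the eosinophil check to anyone, and the one route open to the site shows it the hidden count. A permissive rule still needs its input.

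A reader might also infer that the criterion lowers the transaminase threshold for eosinophilic asthma, since "The study will also aim to randomize a similar percentage of subjects with" eosinophils below and above 300/µL (Section 4.1), or that placebo subjects would meet it more readily. The text does not support either reading. Section 7.1 speaks of the feature appearing, which implies new onset, and the Visit 3 pre-dose count is unredacted and serves as the comparator. The protocol sections on background and endpoints do not state a fall in eosinophil counts on tezepelumab.

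**Conclusion.** The point holds in a narrow form. One limb of one liver criterion cannot be assessed from the results the protocol supplies, because Section 7.1 calls for a value that the Schedule of Activities redacts and no one else is assigned to read. This follows from current text and needs no assumption beyond the remaining differential being reported to the site.

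The consequence is small. It touches a fraction of perhaps 5 to 21 subjects, a range resting entirely on the assumed 0.5% to 2%. The other liver criteria are intact, and neither bias in the primary result nor any change to sample size, power or alpha is claimed. It still merits correction, because it is a subject-safety rule and the repair is cheap.

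**What to change.** In Protocol Appendix E 3, add to the central alert:

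> *For a randomized subject with ALT or AST ≥3×ULN, the central laboratory (or an unblinded reviewer outside the study team) applies the ≥5% eosinophil test to the haematology sample of the same visit and sends the site only: eosinophilia criterion met / not met / not available. Counts stay redacted.*

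Cross-refer to this in the fourth liver criterion of Section 7.1. The site holds the Visit 3 pre-dose value, so it can judge whether a met result is new. Subjects already at ≥5% at Visit 3 should not be carved out; that would be a medical change the documents do not support.

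The cost is wording in two places and one programmed field. No extra scheduled samples are needed, because Table 2 has haematology at every visit with serum chemistry (Weeks 0, 12, 24, 36, 52 and 64, IP discontinuation and unscheduled). Where E 3 requests a central repeat after a local result, the repeat should include haematology; otherwise the flag reads not available. The downside is that the flag gives the site slight information about one subject's eosinophils, much less than a local differential would.

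If the sponsor's physicians see no value in an eosinophil trigger in this population, deleting that limb from Section 7.1 is simpler and equally consistent.
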